14.5 IRB Approvals

HIC#: 1603017415 Protocol version 11.0

No subjects are to be entered on study without full IRB approval. IRB re-approval must be appropriately maintained. Documentation of reapproval must be obtained in a timely manner or registration will be halted.

14.6 Amendments and Consents

The Study Coordinator will maintain a copy of all amendments, consent forms, and approvals. Consent forms will be reviewed and approved by the Yale IRB. Should changes to the protocol or consent become necessary, protocol amendments will be issued by the Yale IRB.

15.0 DATA ANALYSIS / STATISTICAL METHODS

The analyses and methods described in this section, for this randomized, Phase II, single-blinded, 3-arm clinical trial, apply to the primary, secondary, and exploratory/correlative objectives provided in Sections 1.1 to 1.3

15.1 General Statistical Considerations

- Type I error for hypothesis testing will be $\alpha = 0.05$, and 95% confidence intervals will be used for parameter estimation, unless otherwise specified. Type II error will be based on $\beta = 0.10$, unless otherwise specified. Only the primary analysis will use an adjustment for multiple comparisons.
- Summary statistics for continuous variables will include (but may not be limited to) the number of observations, mean, standard deviation, minimum, median and maximum. For categorical variables, summary statistics will include (but may not be limited to) counts, percentages, and cross-tabulation tables.
- Standard diagnostics will be performed to assess whether the assumptions for specific parametric statistical methods are adequately supported by the data. Should parametric methods be inappropriate, the analogous non-parametric methods will be used and only these results will be reported.
- Imputation of missing values will not be applied.
- No interim analyses for efficacy or futility are planned, although the trial may be stopped early based on observations from continual safety monitoring.
- Data analysis will be conducted using SAS® v9.4 (or later).

15.2 Analysis Set Definitions

- **full analysis set**—all randomized subjects
- safety analysis set—all subjects who have received at least one dose of any study drug, and/or have had any assessments at baseline or later that could be associated with an AE; analyzed by treatment received
- ITT analysis set—all randomized subjects with valid baseline measurements; analyzed by treatment assigned
- modified ITT analysis set—all randomized subjects with valid baseline measurements, receiving at least one dose of any study drug, and have at least one valid post-baseline measurement of outcome; analyzed by treatment assigned

HIC#: 1603017415 Protocol version 11.0

- modified ITT completers analysis set—all randomized subjects who receive at least one dose of
 any study drug and have complete and valid post-baseline assessments of outcome; analyzed by
 treatment assigned
- **per protocol analysis set**—all randomized subjects who receive all doses of their assigned study drug, have complete and valid post-baseline assessments of outcome, and have no protocol deviations (e.g. dose modification, assessment outside of time window, non-compliance)

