6.0 TREATMENT PLAN AND ENTRY PROCEDURE/REGISTRATION PROCEDURE

HIC#: 1603017415 Protocol version 11.0

6.1 Study Entry: Subjects will be screened and consented by the P.I. or a member of the study staff. Consent may be obtained remotely. The consent form can be mailed or emailed to the research participant who will sign a printed version of the consent form and fax/scan/email/send a picture of the signed consent form or mail the signed consent form back to the researcher.

[figure not shown]

FIGURE 1: Study Timeline

6.2 Treatment Plan This is a randomized Phase II, three arm control trial in subjects with CIN 2/3 high grade cervical dysplasia. Subjects with CIN 2/3 meeting eligibility criteria will have cervical biopsy specimens centrally reviewed by study pathologist to confirm diagnosis. HPV DNA test and HPV 16/18 genotyping will be performed from endocervical cytobrush samples to determine HPV status associated with the dysplasia.

Subjects who have CIN 2/3 with HPV+ disease will be enrolled in this study. Subjects will be randomized to one of three arms: observation only (control), imiquimod only, imiquimod + 9-valent HPV vaccine. All cytology and cervical biopsy specimens related to the study will be centrally reviewed by study pathologists who will be blinded to treatment assignment.

6.2.1 Pre-Treatment Visit/Study Enrollment: After the index cervical biopsy demonstrating CIN 2-3, all subjects will be brought back to clinic to discuss results and management. After obtaining informed written consent the following pre-treatment tests will be performed: medical history, physical exam with pelvic exam, vital signs, urine pregnancy test (must be performed within 7 days of treatment), translational blood

HIC#: 1603017415 Protocol version 11.0

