samples (may be drawn after randomization but must be drawn prior to treatment), endocervical specimen to be sent to Yale Pathology for high-risk HPV DNA testing (if high-risk HPV DNA results are already available, this testing may not have to be repeated) and a second endocervical cytobrush specimen for translational research purposes. Blood samples will be collected in sodium heparin tubes with about 28 cc collected each time as follows: 7 cc in each of 3 green top tubes and 7 cc in 1 EDTA/purple top tube (see follow up visits below). Endocervical specimen for high-risk HPV DNA test to be performed by Yale Pathology will be submitted in usual fashion as a SurePath specimen. Endocervical cytobrush sample for study purposes will be collected into a 50ml conical tubes containing PBS using sterile techniques and will be stored on ice until picked up by a laboratory personnel. Once all eligibility has been met the subject will be randomized to one of three arms.

Additional components of visit outline by study group:

- (1) Control group: Observation at specified study timepoints.
- (2) Imiquimod only: At the baseline visit, this group will receive instruction on imiquimod self application (16 week course) using a 6.25 mg vaginal suppository, storage of medication, possible side effects. Subjects will be provided a diary and case report form to record vaginal suppository application and side effects will be recorded per NCI Common Terminology Criteria for Adverse Events (CTCAE 4.0). Imiquimod self-application regimen will be similar to one previously described²⁴ and is as follows:
- Treatment weeks 1 and 2: Subjects apply one vaginal suppository per week
- Treatment weeks 3 and 4: Subjects apply two vaginal suppositories per week
- Treatment weeks 5 to 16: Subjects apply three vaginal suppositories per week

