15.5 Analysis for the Primary Objective

The co-primary objectives of this study are to test superior treatment efficacy of Imiquimod + HPV vaccine (Trt1) compared to control (Trt0), and likewise Imiquimod only (Trt2) compared to control (Trt0). The primary outcome is *histologic regression* (yes/no) after completion of the 12 to 16 weeks imiquimod course. The full definition of *histologic regression* and how it is determined is described in Section 5.1.

The co-primary hypothesis tests are:

 $\{H_{01}: p_1 - p_0 = 0 \text{ versus } H_{11}: p_1 - p_0 > 0\}$ and

 $\{H_{02}: p_2 - p_0 = 0 \text{ versus } H_{12}: p_2 - p_0 > 0\}$

 p_0 , p_1 , and p_2 are the proportion of subjects on Trt0, Trt1, and Trt2, respectively, who are determined to have *histologically regressed*. Fisher's Exact Test will be used to assess if the data support rejecting the null hypothesis H_{01} , and likewise for H_{02} . To control Type I error, we will use a conservative Bonferroni adjustment for multiple comparisons with one-sided $\alpha = (0.05)/2 = 0.025$ as the significance level for each test. Rejection of a particular null hypothesis suggests superior efficacy of that specific treatment compared to control. Exact 95% confidence intervals will be calculated for p_1 - p_0 and for p_2 - p_0 . Confidence intervals for 'risk ratios' (p_1/p_0 , p_2/p_0) in addition to 'risk differences' (p_1 - p_0 , p_2 - p_0) may also be estimated. The main analysis will use the **modified ITT analysis set**. Sensitivity analyses for the same statistical method using the **modified ITT completers** and/or **per protocol analysis sets** may also be provided.

HIC#: 1603017415 Protocol version 11.0

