Exact binomial probabilities for α given minimum required power = (1- β)								
Δ =	0.00	0.10	0.20	0.30	0.32	0.35	0.37	0.40
(1-β) ≥ 0.80	0.8080	0.8008	0.8101	0.8126	0.8011	0.8168	0.8119	0.8113
α =	0.5321	0.7745	0.1537	0.0366	0.0220	0.0118	0.0058	0.0027
(1-β) ≥ 0.90	0.9033	0.9009	0.9049	0.9060	0.9068	0.9062	0.9012	0.9009
α =	0.4835	0.6574	0.2876	0.0863	0.0616	0.0363	0.0203	0.0103
Exact binomi	Exact binomial probabilities for power = $(1-\beta)$ given maximum required α							
Δ =	0.00	0.10	0.20	0.30	0.32	0.35	0.37	0.40
α ≤ 0.025	0.0147	0.0147	0.0143	0.0140	0.0140	0.0143	0.0146	0.0149
1-β =	0.0147	0.1050	0.3472	0.6860	0.7472	0.8269	0.8706	0.9215
α ≤ 0.05	0.0305	0.0327	0.0272	0.0304	0.0317	0.0330	0.0331	0.0323
1-β =	0.0305	0.1795	0.4847	0.7870	0.8328	0.8898	0.9197	0.9535

Software: G*Power version 3.1.9.2, ©1992-2014, Franz Faul, Universität Kiel, Germany

At 7-8 months from time of initial CIN 2,3 diagnosis, persistent or progressing dysplasia will be surgically excised per current standard of care. Risk of progression of high-grade cervical dysplasia during the study period in the observation group is very low and observation periods of 6-9 months for CIN 2,3 are commonly described in the literature.^{24,39} In this regard, studies estimating the risk of clinical progression from CIN2/3 lesions to cervical cancer found that the median time was 23.5 years with only 1.6% of these lesions becoming invasive within 10 years⁴⁰. In addition, any clinical concern for disease progression based on history, physical exam or colposcopy at an interval follow up visit will trigger cervical biopsies to objectively evaluate histopathology and, should disease progression be noted, the subject will be removed from study and offered surgical excision. We will also employ early stopping rules as follows:

Evaluability for Efficacy and Toxicity:

Only those subjects who are deemed "ineligible" will be eliminated from the analysis. All subjects who receive any therapy will be evaluated for both treatment efficacy and toxicity. While on occasion, circumstances may prevent the determination of treatment efficacy, such subjects will be included in the

HIC#: 1603017415 Protocol version 11.0

analysis and labeled as "unknown". This category will be listed and be reflected in the calculation of the response rate.

References

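### The modified ITT set requires a dose of study drug, so as written it excludes every observation-only control from the main efficacy analyses

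*Combined protocol and SAP*

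**What the plan says.** Section 15.2 admits a randomized subject to the modified ITT set on three cumulative conditions: valid baseline measurements, then "receiving at least one dose of any study drug, and have at least one valid post-baseline measurement of outcome; analyzed by treatment assigned". No arm is exempted. The modified ITT completers set carries the same dose condition. The per protocol set is built from "all randomized subjects who receive all doses of their assigned study drug". The safety set, in the same list, has an alternative route for undosed subjects: "and/or have had any assessments at baseline or later that could be associated with an AE".

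For the co-primary comparisons, section 15.5 states: "The main analysis will use the modified ITT analysis set". Sections 15.6 and 15.7 name the same set for histologic remission, HPV clearance and the exploratory analyses. The ITT and full analysis sets have no dose condition, but neither is assigned to an efficacy analysis; ITT is used only for the baseline summaries in section 15.4.

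Section 6.2 lists the arms as "observation only (control), imiquimod only, imiquimod + 9-valent HPV vaccine", and section 6.2.1 describes control as "1) Control group: Observation at specified study timepoints". Section 4.0 describes two products only, imiquimod and the 9-valent vaccine.

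The evaluability text at the end of section 15.8 says "Only those subjects who are deemed 'ineligible' will be eliminated from the analysis" and then "All subjects who receive any therapy will be evaluated for both treatment efficacy and toxicity". It also keeps subjects whose efficacy cannot be determined in the analysis, in an unknown category that is reflected in the response rate. Section 15.1 rules out imputation.

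**The concern.** Controls receive no study drug by design, so none can meet the modified ITT definition. Both co-primary hypotheses and both secondary efficacy outcomes are contrasts with control. Followed as written, they cannot be estimated, and the optional completers set fails in the same way.

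Nobody would analyse the trial with an empty control arm. The practical risk is that the analyst has to replace the written rule with one the plan does not state, possibly after outcomes are known. The candidate rules can give different denominators: delete the dose condition for all arms, waive it for control only, or switch to ITT.

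The control-only waiver is the easy repair, and it is asymmetric. A subject who never doses but returns for the week 20–24 biopsy would be dropped from a drug arm and kept in control. Subjects probably know their arm: blinding is described only for the pathologists (sections 5.1 and 6.2) and no placebo is described, although section 15.0 calls the trial single-blinded. Failure to start could therefore depend on the arm. The exposure lies mainly in the imiquimod-only arm, where treatment is self-applied at home; the vaccine arm is dosed in clinic on day 1 (sections 4.2.2 and 6.2.1).

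**Working it through.** **1. The plan's own figure.** Inputs from sections 15.5 and 15.8: control rate 0.28, effect 0.35 (so 0.63 on treatment), 38 per arm, Fisher's exact test at one-sided 0.025. Enumerating both binomials and rejecting when the hypergeometric tail is at most 0.025 gives power 0.8269, equal to the value in the operating-characteristics table. That table therefore presumes 38 controls in the analysis.

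**2. Literal reading.** Controls with at least one dose by design = 0, so 0 of 38 evaluable (0 of 46 recruited) enter the modified ITT set. The control proportion has no denominator, both differences are undefined, and the test cannot reject.

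**3. Waiver for control only (illustration).** The documents give no non-start rate, so the following are assumptions. Let q be the share of the imiquimod-only arm that never starts and r the share of those who return for biopsy. Non-starters regress at 0.28, starters at 0.63, and all starters return. With the waiver, the arm's expected rate is 0.63. Without any dose condition it is

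((1 − q) × 0.63 + q × r × 0.28) / ((1 − q) + q × r)

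| q | r | Rate with no dose condition | Overstatement under the waiver |
|---|---|---|---|
| 0.05 | 0.5 | 0.6055 / 0.975 = 0.621 | 0.9 points |
| 0.05 | 1 | 0.6125 / 1 = 0.6125 | 1.75 points |
| 0.10 | 0.5 | 0.581 / 0.95 = 0.6116 | 1.8 points |
| 0.10 | 1 | 0.595 / 1 = 0.595 | 3.5 points |

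If 20% of starters are also lost, (1 − q) becomes 0.8 × (1 − q) and the range moves to 1.1 points (q = 0.05, r = 0.5) up to 4.3 points (q = 0.10, r = 1).

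**4. Missing histology.** This is a separate question that has to be settled in the same definition. Section 15.2 excludes subjects with no post-baseline outcome; section 15.8 keeps them as unknown. Take the plan's 20% dropout in each arm:

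- Unknowns excluded: 0.63 − 0.28 = 0.35. With 46 × 0.8 = 36.8, about 37 per arm, exact power is 0.808.
- Unknowns counted as not regressed: 0.8 × 0.63 − 0.8 × 0.28 = 0.504 − 0.224 = 0.28. With 46 per arm, exact power is 0.745.

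**The case against.** The strongest reply is that the intent is obvious. Section 15.5 defines a control proportion, section 15.8 powers the trial on 38 controls, and its evaluability text removes only ineligible subjects. On that view, 0 of 38 measures a slip of wording and not a risk to the result. The intent is indeed clear, but it does not choose among the possible replacement rules. Nor does section 15.8 amend section 15.2. Its sentence on subjects who receive therapy need not exclude the untreated, so it does not repeat the fault; but by retaining unknowns it conflicts with the requirement for a valid outcome.

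The single mention of placebo in section 15.8 does not supply a dose for controls, because no placebo is described anywhere.

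Three further points carry weight:

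- The per protocol condition can be read as automatically met by an arm that is assigned no drug. It is better called ambiguous than wrong, and the per protocol and completers analyses are optional.
- The non-starter figures rest on assumptions outside the documents and are modest. The standard error of the difference at 38 per arm is √[(0.63 × 0.37 + 0.28 × 0.72) / 38] = 0.107, or 10.7 points.
- The larger contrast, 35 against 28 points, comes from the missing-histology conflict and would remain if the dose wording were perfect. It should not be counted as an effect of the dose condition.

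None of these removes the defect in the definition.

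**Conclusion.** The concern holds. The set named for every main efficacy analysis excludes the whole control arm as written, and no other section corrects it. This needs no assumption beyond control receiving no study drug, which sections 6.2 and 6.2.1 state.

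The bias from a control-only waiver is unknown. The 0.9 to 3.5 points is an illustration for one arm under stated assumptions, and reaches 4.3 points if starters are also lost. The missing-histology rule moves the expected difference by 7 points (35 against 28) at the plan's 20% dropout, assuming equal loss in each arm. The correction must be made before analysis because the primary result cannot be produced from the plan as it stands.

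**What to change.** 1. Delete the dose requirement from the modified ITT and modified ITT completers definitions in section 15.2, so that one rule applies to all three arms, analysed as assigned. Stating that the condition applies only to the drug arms would also make the analysis computable, but it creates the asymmetry described above.
2. In the per protocol definition, state that the all-doses condition applies to the drug arms, and that controls qualify on complete, valid assessments and no deviations.
3. Reconcile the evaluability text in section 15.8 with sections 15.2 and 15.5: say whether subjects without week 20–24 histology are excluded or kept as unknown. If ITT is made the main set instead, state how those subjects count, for example in the denominator as not regressed, because section 15.1 bars imputation. Report the other rule as a sensitivity analysis.

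The first two changes are SAP wording only. Keeping never-dosed subjects may slightly dilute the estimated effect. The third has a real cost only if unknowns count as not regressed: at 20% dropout, power is about 0.745 with 46 per arm, against about 0.81 with unknowns excluded and 37 per arm.

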Imiquimod will be dispensed in boxes containing 18 vaginal suppositories (treatment weeks 1-8) at the beginning of the treatment course. During follow up visit at week 8 (see below), subjects will be provided a new box of 24 vaginal suppositories to complete treatment course for weeks 9-16. Study drug will be prescribed by the investigator and may be dispensed either by the investigator or study staff.

6.2.2 Follow-up Visits: Follow-up visits will occur at week 8 (between weeks 7-9), at week 16 (between weeks 16-18) and once at week 22 (between weeks 20-24). For subjects randomized to treatment arms (2) Imiquimod only and (3) Imiquimod + HPV vaccine, the week 22 visit will occur at least 3 weeks after last dose of therapy. Urine pregnancy test will be performed at all follow-up visits. Subjects with exam findings concerning for worsening disease at any point in the study will be taken out of the study and treated with surgical excision procedure.

Week 8 (7-9 weeks) Visit: This visit will be timed to occur part way through the 16 week imiquimod treatment course. For women using imiquimod (Imiquimod only and Imiquimod + HPV vaccine arms), a review of medication diary, monitoring of correct use of study medication, and report of local and systemic side effects using a standardized case report form will occur at all follow up visits. For women who received HPV vaccine as part of study protocol (Imiquimod + HPV vaccine arm), a review of vaccination diary and report of local and systemic side effects using a standardized case report form will occur at all follow up visits. A pelvic exam with colposcopy will be performed to objectively assess for gross cervical lesions in all subjects and also for local side effects from imiquimod use in the Imiquimod only and Imiquimod + HPV vaccine arms. Endocervical cytobrush samples will be obtained at this time for study purposes. Cervical biopsies will be performed as clinically indicated. Blood sample collections will also occur. In addition, women in the Imiquimod + HPV vaccine groups who were previously unvaccinated will receive their booster dose of the HPV vaccine.

Week 16 (16-18 weeks) Visit: This visit will be timed to occur at completion of imiquimod treatment course. For women using imiquimod (Imiquimod only and Imiquimod + HPV vaccine

HIC#: 1603017415 Protocol version 11.0

CIN 2/3

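### The primary analysis set requires a dose of study drug that observation controls never receive, and its handling of undetermined outcomes conflicts with the Evaluability text in 15.8

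*Combined protocol and SAP*

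**What the plan says.** **Dose condition.** Section 15.2 builds the modified ITT set from joint conditions: randomised, valid baseline, "receiving at least one dose of any study drug, and have at least one valid post-baseline measurement of outcome". The completers set repeats the condition: "all randomized subjects who receive at least one dose of" any study drug. Section 15.5 compares each active arm with control and states: "The main analysis will use the modified ITT analysis set". Sections 6.2 and 6.2.1 list no study drug for the control arm: "Control group: Observation at specified study timepoints". No text exempts controls from the dose condition. Sections 15.6 and 15.7 use the same set.

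**Undetermined outcomes.** Section 15.1 states: "Imputation of missing values will not be applied". With 15.2, a treated subject without a valid post-baseline outcome leaves the main analysis. The Evaluability text at the end of 15.8 says that only ineligible subjects "will be eliminated from the analysis. All subjects who receive any therapy will be evaluated for both treatment efficacy and toxicity". Subjects whose efficacy cannot be determined stay in the analysis, labelled unknown, and "This category will be listed and be reflected in the calculation of the response rate".

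**Removal for worsening.** Under 6.2.2, subjects with exam findings that suggest worsening "at any point in the study will be taken out of the study and treated with surgical excision procedure". Under 15.8, clinical concern first triggers biopsies, and removal with an offer of excision follows if progression is found.

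**The concern.** Both co-primary contrasts, p1 − p0 and p2 − p0, need p0. An analysis set that by its own words contains no controls cannot supply it, so whoever programs the analysis must apply a correction that is not written down.

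The second problem is a choice left open. The same treated subject with no outcome is out of the denominator under 15.2 and in it under 15.8. Both texts are current. Two regression rates can then be computed from one data set, and near the 0.025 boundary they can give different decisions. That choice should be settled before outcomes are seen by arm.

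**Working it through.** **1. Dose condition.** No arithmetic is needed.
- Main set: at least one dose of any study drug (15.2, 15.5).
- Control arm: observation, no study drug (6.2, 6.2.1).
- Literal result: 0 of 46 controls qualify, so neither primary contrast can be computed.
- Contrast: the safety set in the same section also admits subjects through assessments (joined by and/or), so it can include undosed controls. The modified ITT and completers sets have no such route. The per protocol set asks for all doses of the assigned drug, which has no clear meaning for a control.

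**2. Inputs for the denominator question.** From 15.5: one-sided Fisher's exact test at 0.025 for each comparison. From 15.8: control rate 0.28, difference 0.35 (so 0.63), 38 evaluable and 46 recruited per arm, 20% dropout. Assumptions: 20% of 46 is 9.2, taken as 9 unknown per arm; missingness is unrelated to outcome; unknown means no regression under the 15.8 rule.

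**3. Formula.** For x regressions of n1 on drug and y of n0 on control,

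power = Σx Σy Bin(x; n1, p1) · Bin(y; n0, p0) · 1[p(x, y) ≤ 0.025],

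where p(x, y) is the upper hypergeometric tail given x + y.

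**4. Reproducing the plan.** With n1 = n0 = 38, p1 = 0.63 and p0 = 0.28, the result is 0.8269, the figure in the operating-characteristics table of 15.8.

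**5. Equal unknowns, 9 per arm.** Regressions come from the 37 observed subjects in each arm. The observed rule tests x/37 against y/37; the other tests x/46 against y/46.

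| | Observed only | Unknown as non-regression | Opposite decisions |
|---|---|---|---|
| 63% vs 28% | 0.808 | 0.766 | 4.2% |
| 28% vs 28% | 0.014 | 0.011 | 0.3% |

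Every disagreement is significant on observed outcomes only. Expected difference: 0.35 on observed outcomes, and 0.35 × 37/46 = 0.28 with unknowns as non-regression.

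Example: 23/37 vs 13/37 gives p = 0.018; the same data as 23/46 vs 13/46 give p = 0.027.

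If the number unknown varies at random around 20%, the powers are 0.813 and 0.745. The fixed-count and random-count figures should not be mixed.

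**6. Unequal unknowns (assumed; the documents give no split by arm).**

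| Unknown, drug / control | Power, observed | Power, non-regression | Type I error, observed | Type I error, non-regression |
|---|---|---|---|---|
| 9 / 5 | 0.854 | 0.661 | 0.015 | 0.005 |
| 5 / 9 | 0.837 | 0.896 | 0.014 | 0.023 |

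In the second row the non-regression rule is the more liberal one, although still below 0.025. If losses instead vary at random around 10% on drug and 20% on control, its type I error is 0.029. So whether it exceeds 0.025 depends on the assumed loss pattern.

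**The case against.** The dose condition has only one workable reading. Section 15.5 defines p0 on the control arm and tests against it in this very set, so controls are meant to be in. That stands. A reader might infer that the trial has no valid comparator or that the primary analysis is unsound; the documents do not support that.

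On the denominator, 15.5 names the main set and 15.1 bars imputation, whereas 15.8 never says how unknown subjects enter the rate. That also stands: every figure above for the second rule rests on an assumed reading. Section 15.8 further speaks of occasional cases among subjects who receive therapy, so 20% in every arm is a high scenario. In the equal-loss case the two rules agree in 95.8% of trials at the design effect, and the worked example was chosen at the boundary. What remains is that 15.2 and 15.8 cannot both govern the same subject.

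A reader might also infer that subjects removed for worsening disappear from the analysis and bias it. The documents do not support this. They give no removal counts and no reason to expect one-sided removals without histology. Section 10.11 defines persistent and progressive disease without a time window, so worsening histology from an interim visit already has a non-regression category.

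**Conclusion.** The point holds as a should-fix matter of wording. As written, the modified ITT and completers sets exclude the comparator of both primary tests, although that is plainly not intended. Sections 15.1 and 15.2 conflict directly with 15.8 over treated subjects with no determinable outcome, with 15.5 favouring exclusion.

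Under equal loss of 9 per arm the effect of the conflict is modest: about 4 points of power (0.808 versus 0.766) and opposite decisions in 4.2% of trials at the design effect. This rests on the plan's rates, on missingness unrelated to outcome, and on reading unknown as non-regression. With unequal loss the gap can be much larger and run in either direction. Neither rule is always the conservative one, so it would be wrong to conclude that counting unknowns as failures is the safe default.

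**What to change.** 1. **Section 15.2.** Remove the dose condition from the modified ITT and completers sets in all arms, so that subjects are analysed as randomised. Waiving it for controls alone would drop never-starters from the drug arms only, an asymmetric exclusion after randomisation. Align the reference to receiving any therapy in 15.8, and state how controls enter the per protocol set. Cost: any never-starters with an outcome slightly dilute the drug-arm rates.
2. **Sections 15.5 and 15.8.** Make the Evaluability text agree with the set named in 15.5. Keep observed-outcome modified ITT as the primary denominator, and prespecify unknown-as-non-regression as a sensitivity analysis, before outcomes are examined by arm. Cost: one extra analysis of data already collected, with no added subjects or visits. The primary result still relies on missingness being unrelated to outcome.
3. **Sections 6.2.2 and 15.8.** The two accounts of how removal for worsening is determined must be reconciled.
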